6.7.2. Virologic Rebound

Virologic rebound is defined as:

- At any visit, after achieving HIV-1 RNA < 50 copies/mL, a rebound in HIV-1 RNA to ≥ 50 copies/mL, which is subsequently confirmed at the following scheduled or unscheduled visit; OR
- At any visit, a $> 1 \log_{10}$ increase in HIV-1 RNA from the nadir which is subsequently confirmed at the following scheduled or unscheduled visit.

At any visit after achieving HIV-1 RNA < 50 copies/mL, if the HIV-1 RNA is ≥ 50 copies/mL and < 200 copies/mL, a reflex HIV-1 RNA repeat test will be conducted on stored plasma samples, if available. If the repeat result is < 50 copies/mL, no further action is required. If the repeat result is ≥ 50 copies/mL participants will be asked to return to the clinic for a scheduled or unscheduled blood draw (2 to 3 weeks after the date of the original test that resulted in HIV-1 RNA VR) for confirmation of VR.

A plasma sample from either the first instance or the VR confirmation visit will be tested for HIV-1 capsid genotypic and phenotypic resistance. In addition, if VR is confirmed, a plasma sample from the VR confirmation visit (or from the next available visit) will be tested for HIV-1 PR, RT, and IN genotypic and phenotypic resistance.

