8.5.2. Secondary Analyses

The proportion of participants in Cohort 1 with HIV-1 RNA < 50 copies/mL at Week 26 will be summarized using the US FDA–defined snapshot algorithm.

The analysis window at Week 26 is defined as from Study Day 184 to Study Day 232, inclusive, where Study Day is calculated from the first dose of LEN. Virologic outcome will be defined as the following categories:

- **HIV-1 RNA < 50 copies/mL:** this includes participants who have the last available on-treatment HIV-1 RNA < 50 copies/mL in the Week 26 analysis window
- **HIV-1 RNA \geq 50 copies/mL:** this includes participants
 - Who have the last available on-treatment HIV-1 RNA \geq 50 copies/mL in the Week 26 analysis window, or
 - Who do not have on-treatment HIV-1 RNA data in the Week 26 analysis window and
 - Who discontinue study drug prior to or in the Week 26 analysis window due to lack of efficacy, or
 - Who discontinue study drug prior to or in the Week 26 analysis window due to reasons other than AE, death, or lack of efficacy and have the last available on-treatment HIV-1 RNA \geq 50 copies/mL.
- **No Virologic Data in the Week 26 analysis window:** this includes participants who do not have on-treatment HIV-1 RNA data in the Week 26 analysis window because of the following:
 - Discontinuation of study drug prior to or in the Week 26 analysis window due to AE or death (regardless of whether the last available on-treatment HIV-1 RNA < 50 copies/mL or not) or,

- Discontinuation of study drug prior to or in the Week 26 analysis window due to reasons other than AE, death, or lack of efficacy and the last available on-treatment HIV-1 RNA < 50 copies/mL or,
- Missing data during the window but on study drug.

The proportion of participants in Cohort 1 with HIV-1 RNA < 200 copies/mL at Week 26 will also be summarized using the US FDA–defined snapshot algorithm.

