### 3.8. Analysis Visit Windows

#### 3.8.1. Definition of Key Dates and Study Day

**First Dose Date** for All LEN Analysis is defined as the earliest dose date of either blinded or open-label oral LEN, as recorded on the Study Drug Administration eCRF form.

**Last Dose Date** for All LEN Analysis is defined for participants who prematurely discontinue study drug in any phase (ie, main phase or extension phase) of the study or who complete study drug as the latest dose date of either blinded or open-label oral LEN or SC LEN.

**First Dose Date** for the study is defined as the day when the first dose of blinded study drug (LEN or Placebo) or open-label oral LEN was taken, as recorded on the Study Drug Administration eCRF form.

**Last Dose Date** for the study is defined for participants who prematurely discontinue study drug in any phase of the study or who complete study drug as the latest dose date of any study drug including blinded study drug, open-label oral LEN, and SC LEN.

**First Dose Date of Oral Bridging** is defined for participants who received oral bridging of LEN as the earliest dose date of oral bridging of LEN, as recorded on the Study Drug Administration - Oral Bridging eCRF form.

**Last Dose Date of Oral Bridging** is defined for participants who received oral bridging of LEN, as the latest dose date of oral bridging of LEN before the First Dose Date of Resumed SC Injection, as recorded on the Study Drug Administration - Oral Bridging eCRF form.

**First Dose Date of Resumed SC Injection** is defined for participants who received oral bridging of LEN and resumed the SC injection, as the earliest dose date of SC LEN following the lifting of the Clinical Hold on SC LEN, as recorded on the Study Drug Administration – SC eCRF form.

**Last Study Date** is defined as the latest date of non-missing clinic visits and/or laboratory visits, and/or AE onset and end dates without any imputation, including the 30, 90, and 180-day follow-up visit dates for participants who prematurely discontinue or complete the study.

**Study Day** will be calculated from the First Dose Date, as defined separately above for All LEN Analysis and for the study, and will be derived as follows:

- For postdose study days: Assessment Date – First Dose Date + 1
- For study days prior to the first dose: Assessment Date – First Dose Date

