### **3.8.3. Selection of Data in the Event of Multiple Records in an Analysis Visit Window**

Depending on the statistical analysis method, single values may be required for each analysis window. For example, change from baseline by visit usually requires a single value, whereas a time-to-event analysis would not require 1 value per analysis window.

If multiple valid, nonmissing measurements exist in an analysis window, records will be chosen based on the following rules if a single value is needed:

- For baseline, the last nonmissing value with collection date (and time, if available) on or prior to the first dose date (and time) of study drug will be selected, unless specified differently. If there are multiple records with the same time or no time recorded on the same day, the baseline value will be the average of the measurements for continuous data (except for HIV-1 RNA, see below), or the measurement with the lowest severity (eg, normal will be selected over abnormal for safety electrocardiogram [ECG] findings) for categorical data.
- For postbaseline values (ie, data with collection date [and time, if available] after the first dose date [and time] of study drug):
  - The record closest to the nominal day for that visit will be selected with the exception of CD4 cell counts and CD4% in which the latest record will be selected and HIV-1 RNA level (see below).
  - If there are 2 records that are equidistant from the nominal day, the later record will be selected.
  - If there is more than 1 record on the selected day, the average will be taken for continuous data (except for HIV-1 RNA, see below) and the worse severity will be taken for categorical data, unless otherwise specified.
- For baseline HIV-1 RNA, the latest (considering both date and time) record(s) on or prior to the first dose date and time of study drug will be selected. For postbaseline HIV-1 RNA, the latest record(s) on the window will be selected. For both baseline and postbaseline HIV-1 RNA, if both “HIV RNA Taqman 2.0” and “HIV RNA Taqman 2.0 Repeat” or both “HIV RNA COBAS 6800” and “HIV RNA COBAS 6800 Repeat” are available with the same collection time, the results from the “HIV RNA Taqman Repeat” or “HIV RNA COBAS 6800 Repeat” will be selected for analysis purposes; otherwise, if there are multiple “HIV RNA Taqman 2.0” or “HIV RNA COBAS 6800” records with the same collection time, the geometric mean will be taken for analysis purposes.

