#### **6.2.1. US FDA-defined Snapshot Algorithm**

The analysis window at Week 104 is defined as from Study Day 688 to Study Day 778, inclusive, where Study Day is calculated from the first dose of oral LEN. Participants who have missing HIV-1 RNA at Week 104 and have completed the study before reaching the upper limit of the analysis window for Week 104 will be excluded. All HIV-1 RNA data collected on-treatment will be used in the snapshot algorithm.

HIV-1 RNA on-SC-LEN-treatment is defined as HIV-1 RNA collected up to 28 weeks from the last SC LEN, and on or prior to the first dose of oral bridging of LEN or up to 28 weeks from any resumed SC LEN after oral bridging for participants who received oral bridging of LEN.

HIV-1 RNA on-oral-LEN-treatment is defined as HIV-1 RNA collected after the First Dose Date of Oral Bridging or oral reload after the first SC LEN, and up to 7 days from the Last Dose Date of Oral Bridging for participants who discontinued from the oral bridging of LEN, or up to minimal (Last Dose Date of Oral Bridging +7, First Dose Date of Resumed SC Injection) for participants who resumed SC LEN.

For the snapshot algorithm, HIV-1 RNA on-SC-LEN-treatment will be used. If there is no such result, HIV-1 RNA on-oral-LEN-treatment will be used.

Virologic outcome will be defined as the following categories:

- HIV-1 RNA < 50 copies/mL: this includes participants who have the last available on-treatment HIV-1 RNA < 50 copies/mL in the Week 104 analysis window
- HIV-1 RNA  $\geq$  50 copies/mL: this includes participants
  - Who have the last available on-treatment HIV-1 RNA  $\geq$  50 copies/mL in the Week 104 analysis window, or
  - Who do not have on-treatment HIV-1 RNA data in the Week 104 analysis window and
    - Who discontinue study drug prior to or in the Week 104 analysis window due to lack of efficacy, or
    - Who discontinue study drug prior to or in the Week 104 analysis window due to reasons other than AE, death, or lack of efficacy and have the last available on-treatment HIV-1 RNA  $\geq$  50 copies/mL
- No Virologic Data in the Week 104 analysis window: this includes participants who do not have on-treatment HIV-1 RNA data in the Week 104 analysis window because of the following:
  - Discontinuation of study drug prior to or in the Week 104 analysis window due to AE or death (regardless of whether the last available on-treatment HIV-1 RNA < 50 copies/mL or not) or,

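### SAP 6.2.1 gives conflicting rules for which HIV-1 RNA value counts after oral bridging, and the bridging end dates it relies on (SAP 3.8.1) fit only an episode ended by the first injection after the Clinical Hold

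*SAP*

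**What the plan says.** SAP 6.2.1 contains three instructions on which HIV-1 RNA result decides the Week 104 outcome (Week 156 is handled in the same manner):

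- All data: "All HIV-1 RNA data collected on-treatment will be used in the snapshot algorithm".
- Ranking by route: "For the snapshot algorithm, HIV-1 RNA on-SC-LEN-treatment will be used. If there is no such result, HIV-1 RNA on-oral-LEN-treatment will be used".
- Last value, in the definition of the <50 copies/mL category: "this includes participants who have the last available on-treatment HIV-1 RNA < 50 copies/mL in the Week 104 analysis window". The ≥50 category is worded in the same way.

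The general rule in SAP 3.8.3 agrees with the last-value instruction: "For postbaseline HIV-1 RNA, the latest record(s) on the window will be selected". So does protocol 8.5.2, which sets out the categories for Week 26 and applies the snapshot algorithm to the later weeks: "this includes participants who have the last available on-treatment HIV-1 RNA < 50 copies/mL in the Week 26 analysis window". The protocol ranks nothing by route, and SAP 6.5 declares no change from the protocol's efficacy analyses. The flowchart in SAP Appendix 2 only refers back to 6.2.1.

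Under SAP 6.2.1, a result is on-SC up to 28 weeks from the last SC dose and on or before the first bridging dose, or up to 28 weeks from any SC dose resumed after bridging. For participants who resumed SC, the on-oral period ends at the earlier of the last bridging dose plus 7 days and the resumed SC injection. Those two dates come from SAP 3.8.1. The resumed injection is defined "as the earliest dose date of SC LEN following the lifting of the Clinical Hold on SC LEN". The last bridging dose is defined "as the latest dose date of oral bridging of LEN before the First Dose Date of Resumed SC Injection". The first bridging dose is the earliest one on record and does not depend on the hold. SAP 4.2 uses the first bridging dose and the resumed injection to adjust injection-interval adherence. Protocol 5.4 allows bridging whatever the reason for the missed injection.

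**The concern.** Ranking by route and taking the last value give different answers when an on-SC result and a later on-oral result fall in the same window. The sample taken on the day bridging starts is on-SC by definition. Under the ranking it displaces any later bridging sample, so a re-suppression can be scored ≥50 or a rebound scored <50. Two programmers following the same section could report different outcomes for one participant.

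The date definitions add a separate problem. They work when the first injection after the hold ends the bridging episode. They fail for an episode that starts after that injection: the resumption date then precedes the bridging, the on-oral interval is empty or invalid, and valid on-treatment results are dropped. An earlier value may then stand as the last one, or the participant may fall into the no-virologic-data category. The adherence category in SAP 4.2 is wrong for the same reason.

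**Working it through.** **Inputs.** Day 1 SC is Study Day 15, and the Week 104 and Week 156 windows are Days 688–778 and 1052–1142 (SAP Table 3-1). Bridging starts 26 to 28 weeks (182 to 196 days) after the last injection, and bridging visits are every 10 to 12 weeks (70 to 84 days) (protocol 5.4). A rebound confirmation draw comes 2 to 3 weeks (14 to 21 days) after the first test (protocol 6.7.2).

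**Plan's own figures.** Nominal day = 15 + 7 × week. Week 78 = 561, Week 104 = 743 and Week 156 = 1107, all as in Table 3-1.

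**When the two rules can meet on the nominal calendar.**

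- Bridging start: 561 + 182 to 561 + 196 = Days 743–757.
- Next scheduled bridging visit: 743 + 70 = Day 813 at the earliest, after Day 778.
- Confirmation draw after a viraemic bridging-start sample: 743 + 14 to 757 + 21 = Days 757–778, always inside the window.
- Week 156: bridging starts on Days 1107–1121 and confirmation falls on Days 1121–1142, again inside.

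A scheduled 10-week visit falls inside the Week 104 window only if bridging starts on Days 688–708. With 26-week intervals, that needs earlier bridging of 688 − 561 = 127 to 708 − 561 = 147 days (about 18 to 21 weeks).

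**Example (a), conflicting rules.** Last injection Day 561. Day 743: 120 copies/mL, repeat ≥50, bridging starts. Day 764: <50. Day 743 is on-SC (182 days after injection, not after the first bridging dose). Day 764 is on-oral only (764 − 561 = 203 > 196).

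| Rule | Value used | Outcome |
|---|---|---|
| Route ranking | Day 743 | ≥50 |
| Last on-treatment value | Day 764 | <50 |

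Reversing the values (30 on Day 743, 120 on Day 760) gives <50 by route and ≥50 by last value. That sequence needs a draw the nominal schedule does not supply, such as an unscheduled or early-termination sample. If oral results come first and SC resumes later in the window, the rules agree.

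**Example (b), dates.** Assume earlier bridging from Day 379 to 519, the first post-hold injection on Day 519, bridging again from Day 519 + 182 = 701 (HIV-1 RNA <50), and a viraemic 10-week visit on Day 701 + 70 = 771.

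- On-SC: 771 − 519 = 252 days > 196, so no.
- On-oral: the interval closed by Day 519, so no.

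Day 701 decides the outcome.

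| Change made | Value used | Outcome |
|---|---|---|
| None | Day 701 | <50 |
| Last-value rule only | Day 701 (Day 771 not on-treatment) | <50 |
| Per-episode dates only | Day 701 (on-SC outranks on-oral) | <50 |
| Both | Day 771 | ≥50 |

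The same fault arises with a single episode. Take injections on Days 15, 197, 379, 518 and 748 and weekly oral doses on Days 700–742. If the hold was lifted on Day 300 or 500, the resumed injection is Day 379 or 518. No bridging dose precedes it, so the last bridging dose is undefined. If the hold was lifted on Day 745, the dates work (748 and 742).

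**Adherence (SAP 4.2), example (b) with SC resumed on Day 785.**

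- Literal: (785 − 519) − 182 − (519 − 379) = 266 − 182 − 140 = −56 days, the lowest category.
- Per episode: 266 − 182 − (785 − 701) = 266 − 182 − 84 = 0 days.
- Literal, same spacing but no earlier episode, X being the post-hold injection: 266 − 182 − (X − (X + 182)) = +266 days.

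**Size.** Protocol 1.2.2.2 gives 72 enrolled. If 72 is the denominator, one reclassified participant moves the rate by 1/72 = 1.39 points. For an assumed 2, 3 or 5 participants the shift is 2.8, 4.2 or 6.9 points if all move the same way.

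**The case against.** The section can be read in sequence: on-treatment results are eligible, the ranking picks the pool, and the last value in that pool is classified. SAP 3.8.3 is a general rule, protocol 8.5.2 does not discuss bridging, and putting SC first is an intelligible choice for endpoints counted from the first SC dose. This reading still conflicts with the instruction to use all on-treatment data, and it would be an undeclared departure from the protocol. It also leaves open whether the absence of an SC result is judged within the window or over the whole study.

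On the nominal calendar only the unfavourable error arises, because the confirmation draw is triggered by viraemia. That stands. A rebound scored as <50 needs an off-schedule draw or a shifted calendar.

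On the dates, SAP 2.1.4 reports that bridged participants had been followed until SC resumption or discontinuation, and no later episode is documented. That limits the known impact, but protocol 5.4 still permits later episodes. SAP 6.2.1 does allow for repeated SC resumption on the SC side, but this does not repair the on-oral interval. SAP 4.2 restricts the subtraction to bridging between the two injections being compared. That suggests a per-interval intent, but the dates it then subtracts are still defined once per participant.

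Finally, the endpoint carries no test, and the by-visit tables in SAP 6.3.2 select the latest record, so a rebound would still show there.

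**Conclusion.** The concern holds. SAP 6.2.1 does not settle which result counts for a participant who starts bridging inside the window, and its route ranking departs from the protocol's last-value rule without being declared. The hold-based dates fail for any bridging episode that begins after the first post-hold injection. They work for an episode that this injection ends.

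Misclassification is possible in both directions, but the nominal calendar produces only re-suppression scored as ≥50. The documents do not say how many participants are affected, and the number is probably small: about 1.4 percentage points each, assuming a denominator of 72. Both examples are constructed. The endpoints are secondary and descriptive, so the SAP should be corrected, but the trial's primary conclusion is not at risk.

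**What to change.** 1. In SAP 6.2.1, replace the two ranking sentences with one rule: the last on-treatment HIV-1 RNA in the analysis window is used, whether on-SC or on-oral. Report an SC-only version as a sensitivity analysis.
2. In SAP 3.8.1, define the first bridging dose, last bridging dose and resumed SC injection for each bridging episode, without reference to the Clinical Hold. Resumption is the first SC dose after that episode's first bridging dose. Use these dates in SAP 6.2.1 and 4.2.

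Both changes are needed, as example (b) shows. If the analysis has already been run, the sponsor should document which rule was programmed. The cost is SAP wording and minor reprogramming, with no new data. The reported suppression rate may move slightly in either direction.

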1.2.2.2. GS-US-200-4625 (Week 52)

The study design for Study GS-US-200-4625 is described in Section 3.2. A total of 72 participants are enrolled in 2 cohorts as follows:

- Cohort 1: LEN or placebo to match 600 mg oral on Days 1 or 15 and Days 2 or 16; LEN or placebo to match 300 mg oral on Days 8 or 22.
- Cohort 2: LEN or placebo to match 600 mg oral on Days 1 or 15 and Days 2 or 16; LEN or placebo to match 300 mg oral on Days 8 or 22 in combination with Optimized Background Regimen (OBR).

Week 52 data are available from this study and the main conclusions from this study are as follows:

- Consistent with the data reported in the Week 26 interim analysis, high rates of virologic suppression continued to be maintained through Week 52. These results were consistent even in participants who had suboptimal baseline OBR (eg, low overall susceptibility score, no or 1 fully active agent, integrase strand-transfer inhibitor [INSTI] resistance, no dolutegravir or darunavir), demonstrating a clinically meaningful contribution of LEN towards virologic suppression.
- Consistent with the data reported in the Week 26 interim analysis, there were clinically meaningful increases in CD4 cell count from baseline to Week 52.
- LEN remained generally safe and well tolerated and no new safety information was identified.

For further information, refer to the current edition of the IB.

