In addition, the proportion of participants in Cohort 1 with HIV-1 RNA < 50 copies/mL and < 200 copies/mL at Week 52, and the proportion of participants in combined Cohorts 1 and 2 with HIV-1 RNA < 50 copies/mL and < 200 copies/mL at Weeks 104 and 156 (from the first SC dose of LEN) will also be summarized using the US FDA–defined snapshot algorithm. The analysis window at Week 52 is defined as from Study Day 324 to Study Day 414, inclusive. The analysis window at Week 104 is defined as from Study Day 688 to Study Day 778, inclusive. The analysis window at Week 156 is defined as from Study Day 1052 to Study Day 1142, inclusive. The secondary endpoints will be based on the FAS for the All LEN analysis. Analysis will be based on participants who receive at least 1 dose of SC LEN.

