### 3.8.2. Analysis Visit Windows

For All LEN Analysis, participant’s visits might not occur on protocol-specified visits. Therefore, for the purpose of analysis, observations will be assigned to analysis windows (see Table 3-1).

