  - Discontinuation of study drug prior to or in the Week 104 analysis window due to reasons other than AE, death, or lack of efficacy and the last available on-treatment HIV-1 RNA < 50 copies/mL or,
  - Missing data during the window but on study drug.

The number and percentage of participants with HIV-1 RNA < 50 copies/mL, HIV-1 RNA  $\geq$  50 copies/mL, and reasons for no virologic data at Week 104 will be summarized. The 95% CI for the percentage of participants with HIV-1 RNA < 50 copies/mL will be constructed using the Exact method.

The proportion of participants with HIV-1 RNA < 200 copies/mL at Week 104, and the proportion of participants with HIV-1 RNA < 50 copies/mL and < 200 copies/mL at Week 156 will also be summarized in the same manner using the US FDA-defined snapshot algorithm. The analysis window at Week 104 is defined as from Study Day 779 to Study Day 869, inclusive.

The flowchart of the US FDA-defined snapshot algorithm is provided in Section 12 ([Appendix 1](#)).

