#### **6.5. Changes from Protocol-Specified Efficacy Analyses**

No change from protocol-specified efficacy analysis is planned.

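### SAP 6.2.1 defines the Week 104 snapshot window twice: the second range is the Week 114 window, and the Week 156 window is never given

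*SAP*

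**What the plan says.** SAP 6.2.1 opens its snapshot rules with "The analysis window at Week 104 is defined as from Study Day 688 to Study Day 778, inclusive", counting Study Day from the first oral lenacapavir dose. It attaches a denominator rule to that window: participants with missing HIV-1 RNA who "completed the study before reaching the upper limit of the analysis window for Week 104 will be excluded".

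Near its end, the section extends the algorithm to the 200 copies/mL threshold at Week 104 and to Week 156: "HIV-1 RNA < 50 copies/mL and < 200 copies/mL at Week 156 will also be summarized in the same manner". The next sentence reads "The analysis window at Week 104 is defined as from Study Day 779 to Study Day 869, inclusive". No Week 156 window appears anywhere in 6.2.1.

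Other places bear on the same point:

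- Protocol 8.5.2 gives Week 104 as Days 688 to 778 and says "The analysis window at Week 156 is defined as from Study Day 1052 to Study Day 1142, inclusive".
- SAP Table 3-1 gives Week 104 as 688 to 778, Week 114 as 779 to 869 and Week 156 as 1052 to 1142. SAP 3.8.2 assigns observations to windows by that table.
- SAP 6.5 states "No change from protocol-specified efficacy analysis is planned".

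**The concern.** One section gives two incompatible windows for the same endpoint and none for another endpoint that it covers. The second Week 104 range stands where the Week 156 window would be expected. That it was meant for Week 156 is an inference from its position. If it is right, both the week label and the days are wrong, and correcting the label alone would bring Week 114 data into the Week 156 snapshot.

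Several things depend on the window limits:

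- which last on-treatment HIV-1 RNA value classifies the participant;
- which study completers with missing HIV-1 RNA leave the denominator (SAP 6.2.1);
- the programming rule for participants who have not yet reached the upper limit (SAP Appendix 3, item 8);
- the Week 104 subgroup analyses (SAP 3.4.1 and 6.4);
- the Year 2 data trigger, which is tied to the upper limit of the Week 104 window (SAP 2.1.5).

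**Working it through.** **Inputs.** Day 1 SC falls 14 days after the first oral lenacapavir dose (SAP 1.2), so it is Study Day 15. Nominal days and windows come from SAP Table 3-1. The two competing ranges come from SAP 6.2.1.

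**Step 1: nominal days.** Nominal day = 15 + 7 × week.

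- Week 104: 15 + 728 = 743
- Week 114: 15 + 798 = 813
- Week 156: 15 + 1092 = 1107

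All three match Table 3-1.

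**Step 2: window edges.** The documents do not state how the edges were set. Midpoints between adjacent nominal days reproduce all 13 rows of Table 3-1 from Week 36 to Week 192 exactly. A window starts the day after the midpoint with the previous visit and ends on the midpoint with the next.

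| Visit | Lower midpoint | Upper midpoint | Derived window | Table 3-1 |
|---|---|---|---|---|
| Week 104 | (631 + 743)/2 = 687 | (743 + 813)/2 = 778 | 688–778 | 688–778 |
| Week 114 | (743 + 813)/2 = 778 | (813 + 925)/2 = 869 | 779–869 | 779–869 |
| Week 156 | (995 + 1107)/2 = 1051 | (1107 + 1177)/2 = 1142 | 1052–1142 | 1052–1142 |

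The first Week 104 range in 6.2.1 is reproduced. The second comes out only as Week 114.

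**Step 3: what the stray range covers.** Weeks from Day 1 SC = (day − 15)/7.

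- Day 779: 764/7 = 109.1 weeks
- Day 869: 854/7 = 122.0 weeks

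The only nominal visit inside is Week 114 (Day 813). With the ±6-day visit window of Protocol 6.3.2, an on-schedule Week 104 visit falls on Days 737 to 749, wholly outside. The Week 156 nominal day, 1107, is also outside.

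**Step 4: the denominator rule.** The two upper limits differ by 869 − 778 = 91 days. Take a participant with no on-treatment HIV-1 RNA value in either range who completes the study on Days 778 to 868. Under the first limit that participant has not completed early and stays in the denominator without virologic data. Under the second, the participant is excluded.

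**Step 5: scale.** The Protocol's Week 52 summary says "A total of 72 participants are enrolled in 2 cohorts".

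- Moving one participant between response and non-response shifts the combined proportion by 1/72 = 1.4 points.
- Assumed denominators of 60 or 50 give 1/60 = 1.7 or 1/50 = 2.0 points.
- Dropping one non-responder from n participants with x responders raises the proportion by x/(n − 1) − x/n = x/[n(n − 1)]. This is at most 1/n, reached when x = n − 1, so the same figures are ceilings for the denominator mechanism.

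**The case against.** The best defence is that the plan already resolves the conflict elsewhere. SAP 3.8.2 points to Table 3-1, which is complete. Protocol 8.5.2 gives both windows, and SAP 6.5 declares no departure from it. Three statements agree on Week 104 and two on Week 156, while the stray range misses the Week 104 nominal day and copies an adjacent row. On this view it is an editorial slip in descriptive endpoints, with no test or alpha depending on it.

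That argument shows the intended values can be recovered, and it rules out a deliberate change. It does not make 6.2.1 correct. That section is the specific rule for these endpoints and writes out its own limits without citing Table 3-1. No order of precedence is stated, so a programmer working from it meets two instructions that cannot both be followed.

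Two narrower objections have force:

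- The completer example needs someone with no value in either range. HIV-1 RNA is scheduled at Week 114 and at early termination, so such participants may be few or none.
- The per-participant figures are not an estimate of effect. Denominators at Weeks 104 and 156 may be well below 72, because continuing past Week 52 is optional and some completers are excluded. The Protocol's amendment history mentions only 13 participants still on study at Amendment 5.

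**Conclusion.** The point holds. The second Week 104 sentence in SAP 6.2.1 is wrong as written: it gives the Week 114 window, shares no day with the correct Week 104 window, and occupies the place where the Week 156 window is missing. The values to use are not in doubt, since Table 3-1 and Protocol 8.5.2 agree on 688 to 778 and 1052 to 1142. Nothing in the documents supports a separate window for the 200 copies/mL threshold.

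The firm measure of size is the misplacement: a non-overlapping range, with an upper limit 91 days later than the Week 104 limit. The effect on the proportions is unknown, because the documents do not say how many participants would change category or whether any program used the stray range. The scale of 1.4 to 2.0 points per participant rests on 72 enrolled or on assumed denominators of 60 and 50. The endpoints are secondary and descriptive. It should be fixed, but it does not threaten the trial's main conclusion.

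**What to change.** In SAP 6.2.1, replace the second Week 104 sentence with one stating that the Week 156 window runs from Study Day 1052 to Study Day 1142, inclusive. Changing only the week label would not be enough.

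In the same edit:

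- state that Days 688 to 778 serve both thresholds at Week 104;
- state that the completer exclusion uses Day 778 at Week 104 and, if it is meant to carry over, Day 1142 at Week 156;
- cite Table 3-1 as the source of the limits.

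Then confirm that the snapshot programs use the Table 3-1 limits. The cost is a short SAP correction and a program check, with no new data and no protocol change.
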